Statistical method	
The aim of the study is to demonstrate the non - inferiority of T2259 with regard to Vismed® Multi in terms of performance.
 
The primary performance criterion is the change from baseline of total ocular staining grade in the worst eye on Day 35, evaluated using Oxford 0-15 grading scheme.
 
As the statistical hypothesis is the non-inferiority of T2259 with regard to Vismed® Multi, the main analysis of the primary criterion will be performed in the Per protocol population.
 
A total of 76 patients (i.e. 38 per treatment group) assume at least 90% power to establish the non-inferiority comparison on a one-sided two sample t-test with alpha=2.5 % basis (equivalent to a 95% two-sided confidence interval), assuming that the standard deviation is 2.5 and no difference between the 2 groups with a non-inferiority limit set at 2 for the change in total ocular staining grade.
 
Estimation of the standard deviation and determination of the non-inferiority limit are based upon data of previous studies and literature.
 
Concerning the non - inferiority limit, according to clinicians, a variation of 2 points in the total Oxford grade, which corresponds to a variation of less than 1 grade in the three areas (corneal, temporal and nasal), is considered as not clinically significant.
 
For taking into account approximately 15% of patients non-evaluable in Per protocol analysis (premature withdrawals without performance evaluation, patients with major protocol deviation), a total of 90 patients should be randomised in the study.

Sample size	90 randomised patients.										
Investigation Design	Multicentre, randomised study, investigator-masked, 2 parallel groups (T2259 versus Vismed® Multi) of 38 evaluable patients each.										
Investigation Duration	Run-in-period with preservative free artificial tears (Hydrabak®): from Day 1-10 or Day 1-7 to randomisation visit (Day 1) (one drop in each eye 3 to 6 times daily). 
 ▪ Treatment period: 84 ± 7 days ▪ Total study duration: maximum of 101 days 										

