7.3.3 Secondary performance variables

Secondary performance endpoints analysis will be provided in the PP population and the FAS population.

Same analysis (ANCOVA constructed using main effects of investigation product and baseline score as covariate and descriptive analysis) will be performed on each parameter presented below:

- Change from baseline in Oxford total score at Day 8 and Day 84 in the worst eye and at Day 8, Day 35 and Day 84 in the contralateral eye;

- Change from baseline in OSDI (Ocular Surface Disease Index) total score at Day 8, Day 35 and Day 84;
- Change from baseline in DEQ-5 total score at Day 35 and Day 84;
- Change from baseline in Van Bijsterveld score* (lissamine green staining) total score at Day 8, Day 35 and Day 84;
- Change from baseline in Schirmer Test result* (without anaesthesia) at Day 8, Day 35 and Day 84;
- Change from baseline in TBUT* (Tear Break-Up Time) at Day 8, Day 35 and Day 84.

For conjunctival hyperaemia* using McMonnies photographic scale at Day 8, Day 35 and Day 84, treatment groups will be compared using a Cochran-Mantel-Haenszel (CMH) test based on modified ridit scores, stratified by the baseline value.

Each Dry Eye symptom at Day 8, aDay 35 and Day 84 will be described and compared between treatment group using percentage of patient with an improvement, a stability or a degradation using a chi-2 test.

The total score for the 7 predefined symptoms will be compared between treatment groups using ANCOVA (model from the main analysis).

Performance assessment by the investigator at Day 35 and Day 84 will be described by treatment group. An additional description will be provided in 2 classes (Very satisfactory or satisfactory, not very satisfactory or unsatisfactory) and compared between groups using a Wilcoxon signed-rank test.

Analysis for others parameters will be specified in Statistical Analysis Plan (SAP)

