5 STATISTICAL METHODOLOGY

5.1 Detailed power and sample size

The aim of the study is to demonstrate the non-inferiority of T2259 with regard to Vismed® Multi in terms of performance. The primary performance criterion is the change from baseline of total ocular staining grade in the worst eye on Day 35, evaluated using Oxford 0-15 grading scheme.

As the statistical hypothesis is the non-inferiority of T2259 with regard to Vismed®, the main analysis of the primary criterion will be performed in the Per Protocol population.

A total of 76 patients (i.e. 38 per treatment group) assume at least 90% power to establish the non-inferiority comparison on a one sided two sample t test with $\alpha=2.5\%$ basis (equivalent to a 95% two sided confidence interval), assuming that the standard deviation is 2.5 and no difference between the 2 groups with a non-inferiority limit set at 2 for the change in total ocular staining grade.

Estimation of the standard deviation and determination of the non-inferiority limit are based upon data of previous studies and literature.

Concerning the non-inferiority limit, according to clinicians, a variation of 2 points in the total Oxford grade, which corresponds to a variation of less than 1 grade in the three areas (corneal, temporal and nasal), is considered as not clinically significant.

For taking into account approximately 15% of patients non-evaluable in Per protocol analysis (premature withdrawals without performance evaluation, patients with major protocol deviation), a total of 90 patients should be randomised in the study.

The non-evaluable patient rate was based on the previous studies major deviations and missing data. For this study, missing data are higher than planned (partially due to Covid-19 pandemic) and the number of randomised patients is 101 to maintain approximately the number of 76 patients evaluable in the Per Protocol.

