5.2 Generalities for statistical analyses

After the database lock and the randomisation code release, the statistical analysis will be performed by the statistician of Axonal-Biostatem, using SAS® software v9.4 (GUIDE, SAS Institute, North Carolina, USA), according to this SAP.

Disposition and baseline characteristics will be presented overall (globally) and by treatment groups. Performance and safety assessments and exposure/compliance will be presented by treatment groups.

Continuous variables will be summarised using descriptive statistics (number of non-missing data (n), number of missing observations, mean, standard deviation (SD), median, lower quartile (Q1), upper quartile (Q3), minimum and maximum).

Except minimum and maximum, descriptive statistics will be presented with one more decimal than the recorded value.

To compare treatment groups for ordinal qualitative variables, Cochran-Mantel-Haenszel (CMH) test will be used stratified by baseline values (if mentioned), with modified ridit scores and “row mean score differ” option. To compare treatment group when variable will be quantitative, Student T-test will be used, when data distribution will be assumed as normal (Shapiro-Wilk test for normality). If it is not the case, Mann-Whitney Wilcoxon test will be preferred instead.

Quantitative parameters will be also compared between groups using ANCOVA model. Furthermore, the mean change from baseline in total staining grade in the worst eye at Day 35 will be compared between the two treatments based on the MMRM analysis, which assumes:

- Data are Missing At Random (MAR)
- All the available data provide the information about non-observed data
- The treatment effect assume that the withdrawn patients mimic those who continued

Assumptions underlying the ANCOVA (respectively MMRM for the sensitivity analysis) will be checked:

- A histogram of residuals will be plotted to check the assumption of normality
- The underlying assumptions of normality of residuals will also be checked by using Shapiro-Wilk test
- Normal probability plot and QQ-plot will be performed to check the assumption of normality
- Residuals will be plotted against predicted values to check the assumption of heteroscedasticity
- For ANCOVA models, Levene's test will also be performed to check the homogeneity of variances

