covariate. The LS ("adjusted") means for each treatment arm and estimates of the difference between groups (T2259 – Vismed® Multi) will be presented along with the respective two-sided, 95% CI. Two-sided p-values will be presented for the treatment difference.

- OSDI (Ocular Surface Disease Index) total score

Each question (from Q1 to Q12) will be presented, by treatment group, by frequency and percentage at each time point (D1, D8, D35 and D84). Total score and change from baseline will be tabulated, by treatment group. These analyses will be performed at Day 8, Day 35 and Day 84.

Change from baseline in OSDI total score will be analysed at D8, D35 and D84 using an ANCOVA model, constructed using main effects of investigation product and baseline score as covariate. The LS ("adjusted") means for each treatment arm and estimates of the difference between groups (T2259 – Vismed® Multi) will be presented along with the respective two-sided, 95% CI. Two-sided p-values will be presented for the treatment difference.

Moreover, at each time point, OSDI total score will be presented, by treatment group, by frequency and percentage with the following modalities: Normal ([0-13[]), Mild ([13-23[]), Moderate ([23-33[]) and Severe ([33-100]) and Cochran-Mantel-Haenszel (CMH) test will be performed for D35 and D84.

- Schirmer Test result* (without anaesthesia)

Schirmer test results at each time point (D1, D8, D35 and D84) and change from baseline will be tabulated, by treatment group. These analyses will be performed at Day 1, Day 8, Day 35 and Day 84 on both worst and contralateral eye.

Change from baseline in Schirmer Test result will be analysed at D8, D35 and D84 on both worst and contralateral eye using an ANCOVA model, constructed using main effects of investigation product and baseline score as covariate. The LS ("adjusted") means for each treatment arm and estimates of the difference between groups (T2259 – Vismed® Multi) will be presented along with the respective two-sided, 95% CI. Two-sided p-values will be presented for the treatment difference.

*Assessment recorded for each eye will be analysed for the worst eye and the contralateral eye.

- TBUT* (Tear Break-Up Time)

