Each measure of TBUT will be presented, by treatment group, by frequency and percentage at each time point. Mean TBUT at each time point (D1, D8, D35 and D84) and change from baseline will be tabulated, by treatment group for both worst and contralateral eye. These analyses will be performed at Day 8, Day 35 and Day 84.

Change from baseline in mean TBUT will be analysed at D8, D35 and D84 on both worst and contralateral eye using an ANCOVA model, constructed using main effects of investigation product and baseline score as covariate. The LS ("adjusted") means for each treatment arm and estimates of the difference between groups (T2259 – Vismed® Multi) will be presented along with the respective two-sided, 95% CI. Two-sided p-values will be presented for the treatment difference.

- Conjunctival hyperaemia* using McMonnies photographic scale

Score of Conjunctival hyperaemia will be tabulated, by treatment group, at each time point

(D1, D8, D35 and D84) using frequency and percentage. Treatment groups will be compared using a Cochran-Mantel-Haenszel (CMH) test based on modified ridit scores (using SCORES=MODRIDIT option in FREQ procedure), stratified by the baseline value.

*Assessment recorded for each eye will be analysed for the worst eye and the contralateral eye.

- Dry eye symptoms

Each Dry Eye symptom at Day 8, Day 35 and Day 84 will be compared between treatment group using percentage of patient with an improvement, a stability or a degradation from baseline using a Cochran-Mantel-Haenszel (CMH) test.

Total score and change from baseline will be tabulated, by treatment group. These analyses will be performed at Day 8, Day 35 and Day 84.

Change from baseline in Dry Eye Symptoms total score will be analysed at D8, D35 and D84 using an ANCOVA model, constructed using main effects of investigation product and baseline score as covariate. The LS ("adjusted") means for each treatment arm and estimates of the difference between groups (T2259 – Vismed® Multi) will be presented along with the respective two-sided, 95% CI. Two-sided p-values will be presented for the treatment difference.

- Performance assessment

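### Each dry-eye symptom is tested as improved/stable/worse without stratifying by its Day 1 grade: a valid but inefficient secondary test, when the SAP's own hyperaemia method would use the data better

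*SAP*

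**What the plan says.** Seven symptoms are each graded 0 to 3 (SAP 3.1.2). They are asked about at Day 1, at the optional Day 8 visit, and at Days 35 and 84 (Protocol 6.4.2 to 6.4.5).

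- **Protocol 7.3.3** compares each symptom "using percentage of patient with an improvement, a stability or a degradation using a chi-2 test".
- **SAP 4.3** replaces that chi-square test with a CMH test. **SAP 6.7.2** keeps the three classes and compares the arms "using percentage of patient with an improvement, a stability or a degradation from baseline using a Cochran-Mantel-Haenszel (CMH) test".
- **SAP 5.2** gives the general rule for ordinal variables: a CMH test with modified ridit scores and the row-mean-scores statistic, "stratified by baseline values (if mentioned". The symptom text names no baseline stratum, so the symptom test is unstratified.
- **SAP 6.7.2, hyperaemia**, immediately before the symptoms, tests the grade itself by modified-ridit CMH stratified by its baseline value.
- **SAP 6.7.2, OSDI classes** (Normal, Mild, Moderate, Severe): "Cochran-Mantel-Haenszel (CMH) test will be performed for D35 and D84", again with no stratum named.
- **SAP 6.7.2** also plans ANCOVA with the baseline score as covariate for the symptom total and the OSDI total.

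**The concern.** Collapsing the change to three classes discards its size: 3 to 0 and 3 to 2 are both an improvement. It also builds in floor and ceiling effects. A patient at grade 0 can only stay or worsen, and one at grade 3 can only stay or improve. The class a patient can reach therefore depends on the starting grade, and an unstratified test leaves that variation as noise. Randomisation is stratified by site only (SAP 2.4), so chance alone balances the seven baseline grades.

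At stake is the power of the item-level symptom comparisons: 7 symptoms x 3 visits = 21 tests, in each of the PP and FAS populations. Protocol 4.1 names stinging, itching and blurred vision among the expected benefits, and a total score cannot show which symptom differs.

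**Working it through.** **1. The plan's own figure.** The only power statement concerns the primary endpoint: "A total of 76 patients (i.e. 38 per treatment group) assume at least 90% power", "assuming that the standard deviation is 2.5 and no difference between the 2 groups with a non-inferiority limit set at 2", on a "one-sided two sample t-test with alpha=2.5 % basis (equivalent to a 95% two-sided confidence interval".

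- n per arm = 2 x (1.960 + 1.282)² x 2.5² / 2² = 32.8, so 33 by the normal formula (34 with the exact t).
- At 38 per arm: SE = 2.5 x √(2/38) = 0.574; 2/0.574 − 1.960 = 1.53; power 93.7% (93.1% with the noncentral t).
- With "approximately 15% of patients non-evaluable in Per protocol analysis": 76/0.85 = 89.4, so 90 randomised.

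The primary sizing reproduces and is not in question. It gives 38 per arm as a realistic size for the symptom tests. No power is stated for them.

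**2. Symptom tests, latent-scale model.** The documents give no symptom distributions, effects or correlations, so these inputs are assumptions:

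- baseline grades 0/1/2/3 of 15/30/35/20% (mixed), 35/30/25/10% (mild-heavy) or 5/20/45/30% (severe);
- a 0.5 SD improvement in both arms and a further 0.6 SD in one arm;
- baseline-to-visit correlation 0.3, 0.5 or 0.7;
- 38 per arm, two-sided 5%, 2,500 simulated trials per setting.

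The N ratio is ((1.960 + z of new power)/(1.960 + z of planned power))². For the mixed case at 0.5 it is (2.546/1.865)² = 1.86.

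| Baseline | Correlation | Planned: 3 classes, unstratified | 3 classes, stratified by Day 1 grade | 0-3 grade, stratified by Day 1 grade | N ratio |
|---|---|---|---|---|---|
| Mixed | 0.3 | 36.4% | 52.6% | 63.5% | 2.04 |
| Mixed | 0.5 | 46.2% | 60.4% | 72.1% | 1.86 |
| Mixed | 0.7 | 58.7% | 72.2% | 81.4% | 1.71 |
| Mild-heavy | 0.3 | 24.9% | 45.8% | 55.0% | 2.65 |
| Mild-heavy | 0.5 | 29.0% | 54.1% | 62.0% | 2.59 |
| Mild-heavy | 0.7 | 37.2% | 60.1% | 70.8% | 2.36 |
| Severe | 0.3 | 43.9% | 54.5% | 67.6% | 1.79 |
| Severe | 0.5 | 55.2% | 62.6% | 73.3% | 1.53 |
| Severe | 0.7 | 70.7% | 75.6% | 84.4% | 1.41 |

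The gain from the planned test to the last method runs from 14 points (84.4 − 70.7) to 34 (70.8 − 37.2). Stratifying the three classes alone gives about 5 to 25 of those points. With no true difference, every method rejected in about 4 to 6% of trials.

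**3. Symptom tests, grade-shift model.** Visit grade = 0.7 x baseline + constant + N(0, 0.8) − shift, rounded and truncated to 0-3, with 38 to 45 per arm. Gains by assumed shift:

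- 0.2 grade: about 2 to 5 points (for example 12.9% to 15.1% at 38 per arm);
- 0.35 grade: about 6 to 12 points;
- 0.5 grade: about 10 to 20 points. One baseline mix (25/35/30/10%, 45 per arm) went higher, from 40% to 65%.

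**4. Day 8.** The visit is optional (SAP 2.1). With an assumed 10 patients per arm, stratification gained 0 to 4 points and power stayed below 20% by either method.

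**5. OSDI classes.** Entry requires OSDI of at least 23 (SAP 2.2.1), so eligible patients start in only two classes, Moderate or Severe. Assumptions: SD 18, mean 40 or 50 before truncation, a 12-point fall in both arms, a 10-point difference between arms, 38 per arm, 6,000 trials per setting. Power, unstratified to stratified by Day 1 class:

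- mean 40: 58.4 to 58.5%, 63.4 to 65.7% and 67.5 to 74.4% at correlations 0.3, 0.5 and 0.7;
- mean 50: 54.2 to 54.6%, 57.2 to 58.9% and 61.0 to 66.4%.

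The gain is about 0 to 7 points.

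**The case against.** The strongest reply is that the baseline-adjusted, full-range comparison is already planned where it matters most. OSDI, DEQ-5 and the symptom total each have ANCOVA with baseline as covariate, adjusted means and confidence intervals. The criticised tests are item-level breakdowns and a supplementary class table. SAP 5.4 treats all non-primary endpoints as secondary and unadjusted, and no sample size rests on them. This stands, and it limits the importance of the point. It does not remove it, because the totals do not show which symptom differs.

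Second, the size depends on assumed effects. The trial is planned for non-inferiority with no assumed difference, so a half-grade benefit may be optimistic; at 0.2 grade the gain is small. This also stands, so the size is given as a range.

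Third, the percentages improved, stable or worse are easy to read, and the planned test matches what is displayed. That is a fair reason to keep them as description. After the change, the p-value tests the visit grade given baseline, not the displayed percentages.

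A reader might also infer that the symptom tests are biased by baseline imbalance. The documents do not support that: allocation is randomised 1:1, the classes are within-patient changes, and simulated type I error was about 5%. Nor do they support reading the OSDI-class test as an equal weakness. Only two baseline classes are possible, the gain is small, and the OSDI total has its own ANCOVA.

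**Conclusion.** The point holds as one of efficiency. The per-symptom test drops the size of change and does not adjust for the Day 1 grade, although that grade is collected and the SAP uses the better method for hyperaemia. The direction of the gain was the same in every symptom setting at 38 to 45 per arm. Its size rests on assumed distributions, effects and correlations: about 2 to 5 points of power at a 0.2-grade shift, about 10 to 20 at 0.5, and up to about 34 under the latent-scale model, with little at Day 8.

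It would be wrong to conclude that the patient-reported results as a whole are unadjusted, or that the non-inferiority conclusion is at risk. The totals are baseline-adjusted, and the primary analysis does not use these tests.

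**What to change.** - **SAP 6.7.2, dry eye symptoms:** test each symptom's 0-3 grade at the visit by CMH with modified ridit scores and the row-mean-scores statistic, stratified by that symptom's Day 1 grade.
- Keep the percentages improved, stable and worse as description, with a note that the p-value refers to the visit grade given baseline. SAP 3.3 derives these classes only from the symptom total, so add the per-symptom rule there.
- **SAP 4.3:** record the change before unblinding. If treatment has already been unblinded, report it as an unplanned analysis under SAP 4.2.
- **Optional, for consistency:** stratify the OSDI-class CMH by Day 1 class, or rely on the planned ANCOVA of the OSDI total.

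The cost is a few lines of SAP text and one stratification variable per test. No new data or patients are needed.

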6.8.5 Other measures

6.8.5.1 *Evaluation of Optical Scattering Index (OSI) using double pass aberrometry*

At investigational sites equipped with the Optical Quality Analysis System (OQAS, Vissiometrics, Costa Mesa, CA, USA), evaluation of OSI will be performed at Day 1, Day 35 and Day 84 using the double pass aberrometry to assess the presence of cataract.

The double-pass technique has been shown to be a useful tool for comprehensively evaluating the optical quality of the eye (Logean E *et al.* 2008 ; Santamaría *et al.* 1987). Double-pass systems are based on recording images from a point-source object after reflection on the retina and a double pass through the ocular media. In contrast to wave front aberrometry, the double-pass systems directly compute the modulation transfer function from the acquired double-pass retinal image by Fourier transformation, allowing the complete characterization of the optical quality of the eye, mainly degraded by higher-order ocular aberrations and scattered light. Because of the differences between both technologies, recent studies suggest that wavefront aberrometers may overestimate retinal image quality in eyes where higher-order aberrations and scattered light are prominent (Díaz *et al.* 2006).

6.8.5.2 *Impression cytology (for HLA-DR)*

Samples for impression cytology for HLA-DR will be taken in the right eye (only if right eye is eligible) and only in patients with severe Dry Eye, at Baseline visit (Day 1) and Day 84 (Visit 5) or premature withdrawal, using the **EYEPREM™** sterile medical device.

For sensitive patients, it may be wise to practice a topical anesthesia of the eye. In this case, the anesthesia must be done at Day 1 and Day 84.

Severe Dry Eye is defined as an OSDI score ≥ 33 and/or Corneal Fluorescein Staining ≥ 3 at baseline visit (Day 1).

HLA-DR will be assessed by flow cytometry and expression will be quantified in arbitrary units of fluorescence (AUF) and percentage of conjunctival cell expressing HLA-DR by a central lab.

If the sample taken at baseline is uninterpretable, the sample at Day 84 will not be taken. Furthermore, if a patient discontinues the study before Day 84, a sample will be taken at the discontinuation visit if the baseline sample was interpretable.

One of the most important biological risk concerning cytology impression samples, is the prion disease.

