3.1.2 Secondary performance endpoints

Secondary performance endpoints are:

- Change from baseline in total ocular staining grade according to Oxford grading scheme at Day 8 and Day 84 in the worst eye and at Day 8, Day 35 and Day 84 in the contralateral eye;
- Change from baseline in Van Bijsterveld score* (lissamine green staining) at Day 8, Day 35 and Day 84;
- Change from baseline in DEQ-5 at Day 35 and Day 84;
- Change from baseline in OSDI (Ocular Surface Disease Index) score at Day 8, Day 35 and Day 84;
- Change from baseline in Schirmer test result* (without anaesthesia) at Day 8, Day 35 and Day 84;
- Change from baseline in TBUT* (Tear Break-Up Time) at Day 8, Day 35 and Day 84;
- Conjunctival hyperaemia* using McMonnies photographic scale at Day 8, Day 35 and Day 84;
- HLA-DR (AUF) at Day 84 in Right Eye if eligible eye;
- Objective Scatter Index (OSI) at Day 35 and Day 84;
- Dry Eye symptoms: burning/irritation, stinging/eye pain, itching, eye dryness feeling, foreign body sensation, light sensitivity and fluctuating blurred vision evaluated with a 4-level verbal scale (0 = Absent; 1 = Mild, Present but not disturbing; 2 = Moderate, Disturbing, but not limiting daily activities; 3 = Severe, Very distressing and interfering with daily activities) and change from baseline in total score of Dry Eye symptoms at Day 8, Day 35 and Day 84;
- Performance assessment by the investigator (Unsatisfactory, Not very satisfactory, Satisfactory, Very satisfactory) at Day 35 and Day 84.

*Assessment recorded for each eye will be analysed for the worst eye and the contralateral eye.

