Performance assessment by the investigator will be described by treatment group at Day 35 and Day 84 in 4 classes. An additional description will be provided in 2 classes (Very satisfactory or satisfactory, not very satisfactory or unsatisfactory). Comparison between groups on performance assessment in 4 classes will be performed using a Cochran-Mantel-Haenszel (CMH) test.

For OSI score, only listing will be provided with all corresponding items CRF.

For HLA-DR, quantification (AUF) and percentage will be presented on the whole population. Added analysis will be performed on patients with severe dry eye (OSDI>33 and/or Corneal Fluorescein Staining ≥ 3 at the baseline visit).

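### OSI, a named secondary endpoint, gets only a data listing, and HLA-DR gets by-arm description with no specified baseline-adjusted treatment difference

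*SAP*

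**What the plan says.** SAP 3.1.2 lists both measures among the secondary performance endpoints: "HLA-DR (AUF) at Day 84 in Right Eye if eligible eye" and "Objective Scatter Index (OSI) at Day 35 and Day 84". Protocol 6.3.2 lists the same two. Neither is worded as a change from baseline.

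Day 1 values exist for both. Under Protocol 6.8.5, at equipped sites, "evaluation of OSI will be performed at Day 1, Day 35 and Day 84 using the double pass aberrometry". HLA-DR samples are taken from the right eye if it is eligible, "only in patients with severe Dry Eye, at Baseline visit (Day 1) and Day 84 (Visit 5) or premature withdrawal".

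Protocol 7.3.3 gives no method for either endpoint and leaves the remaining parameters to the SAP. SAP 6.7.2 then says of OSI: "For OSI score, only listing will be provided with all corresponding items CRF". Of HLA-DR it says: "For HLA-DR, quantification (AUF) and percentage will be presented on the whole population". It adds a further analysis in patients with severe dry eye and names no method for it. The planned outputs are Listing 6 for OSI (SAP 8.2), and for HLA-DR Tables 5.40a/b (each timepoint) and 5.41a/b (severe patients, Day 84) in SAP 8.1.

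**The concern.** SAP 6.7.2 writes out an ANCOVA for seven continuous secondary scores: Oxford, Van Bijsterveld, DEQ-5, OSDI, Schirmer, TBUT and total dry eye symptoms. Each has treatment and baseline in the model, an adjusted difference, a 95% CI and a p-value. OSI and HLA-DR are left out although they stand in the same endpoint list and also have a Day 1 measurement.

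For OSI, a reader of the study report would have individual records and no result by arm. For HLA-DR, two programmers following the same SAP could validly produce different outputs: one description only, the other a t-test, a Wilcoxon test or an ANCOVA. That choice should be settled before unblinding. Patients undergo impression cytology and aberrometry for these data, so they should yield a defined result.

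**Working it through.** **1. Is there a planned figure to reproduce?** Only for the primary endpoint. With 38 per arm, SD 2.5, margin 2 and one-sided 2.5%, power is 93.1% by the noncentral t, so the claim of at least 90% holds. Also 76 / 0.85 = 89.4, rounded up to 90. These figures do not bear on OSI or HLA-DR, for which no sample size is stated.

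**2. What is specified for each endpoint**

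| | Seven scored endpoints | HLA-DR | OSI |
|---|---|---|---|
| Pre-treatment value | Yes (DEQ-5 at selection) | Day 1, severe dry eye, eligible right eye (Protocol 6.8.5) | Day 1, equipped sites (Protocol 6.4.2, 6.8.5) |
| Change variable, SAP 3.3 | Yes | None; one rule sets an invalid percentage to missing, none covers AUF | None |
| Model in SAP 6.7.2 | ANCOVA, difference, 95% CI, p | None named | None; listing only |
| Tables in SAP 8.1 | Summaries and ANCOVA | 5.40a/b, 5.41a/b; no ANCOVA | None |

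**3. Does SAP 5.2 fill the gap?** It presents performance data by treatment group, compares quantitative variables by t-test or Mann-Whitney Wilcoxon, and says they are also compared by ANCOVA.

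- OSI: no. The specific sentence in 6.7.2 restricts the output to a listing, which overrides a general rule.
- HLA-DR: partly. By-arm display follows from 5.2, and 7.4.1 limits the Total column to disposition and baseline, so the tables are not pooled. But 5.2 names no covariate for its generic ANCOVA, 6.7.2 does not say whether that rule reaches HLA-DR, and 8.1 lists no matching table.

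**4. Does Table 5.41 duplicate Table 5.40?** Sampling requires OSDI ≥ 33 and/or corneal staining ≥ 3 (Protocol 6.8.5; SAP 2.5, note 5). The severe subset in SAP 6.7.2 uses OSDI > 33 and/or corneal staining ≥ 3. If sampling follows the protocol, the two sets differ only for a patient with OSDI of exactly 33 and corneal staining below 3.

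OSDI = 25 × D / E, with E at most 12 questions. Setting this to 33 gives D/E = 33/25, which needs E to be a multiple of 25. So an unrounded OSDI cannot equal 33. The mismatch matters only if a rounded score is used: D = 16, E = 12 gives 33.33, which rounds to 33 and passes ≥ 33 but not > 33. Apart from that, 5.41 covers the same sampled patients as the Day 84 part of 5.40.

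**5. What precision could be expected?** The number of patients with data is not documented, so n per arm is assumed. In SD units, the half-width of an unadjusted 95% CI is h = t(0.975; 2n − 2) × √(2/n). Adjustment for Day 1 with correlation ρ multiplies variance by 1 − ρ² and h by √(1 − ρ²), ignoring the one degree of freedom spent. At ρ = 0.5, 1 − 0.25 = 0.75 (25% less variance). At ρ = 0.7, 1 − 0.49 = 0.51 (49% less).

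| Assumed n per arm | h, unadjusted | h, ρ = 0.5 | h, ρ = 0.7 |
|---|---|---|---|
| 5 | 2.306 × 0.632 = 1.46 | 1.26 | 1.04 |
| 10 | 2.101 × 0.447 = 0.94 | 0.81 | 0.67 |
| 20 | 2.024 × 0.316 = 0.64 | 0.55 | 0.46 |
| 38 (planned PP size) | 1.993 × 0.229 = 0.46 | 0.40 | 0.33 |

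At 5 to 10 per arm, even an adjusted interval at ρ = 0.5 spans about 0.8 to 1.3 SD on each side.

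**The case against.** The strongest reply concerns HLA-DR. A reader might infer that it has no between-arm analysis, is read without baseline, and cannot be answered. The documents do not support that. SAP 5.2 requires display by arm and supplies generic comparison rules. SAP 7.3 asks for a 95% CI in every continuous summary, and the 7.4.1 template has a p-value column. Tables 5.40a/b cover every timepoint, so Day 1 is shown; only 5.41a/b are confined to Day 84. The endpoint is defined as a Day 84 level, which a by-arm display addresses descriptively, and the secondary objective is only to evaluate. All of this stands. What remains is the missing endpoint-specific adjusted difference and the doubt over whether 5.2 applies.

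For OSI, a reader might infer an undeclared departure from the protocol. That does not follow either: Protocol 7.3.3 deferred the method, so the listing is a prespecified choice. It is also fair that OSI is measured only at equipped sites, sits under other measures, and is described there as a way to assess cataract. This argues for modest claims from the data, but a named endpoint still needs a summary by arm.

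It is also tempting to say that Table 5.41 adds nothing. That goes too far while the method of the severe-only analysis is unstated and the two cut-offs disagree.

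Finally, SAP 5.4 makes no multiplicity adjustment for secondary endpoints, so new models add unadjusted comparisons, possibly in very small groups. That stands as a cost.

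**Conclusion.** The point holds in a limited form. For OSI, the plan followed as written yields no arm-level n, summary or treatment difference. For HLA-DR, it yields by-arm description at Day 1 and Day 84, but no specified baseline-adjusted difference with a 95% CI, and leaves open whether the generic rules in SAP 5.2 apply. Table 5.41 largely repeats the Day 84 part of Table 5.40.

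This is a minor matter: nothing here affects the primary non-inferiority conclusion. The precision figures are illustrative, since both the numbers per arm and the correlations of 0.5 and 0.7 are assumed. They measure the gain from adjustment, not the size of the omission. The overlap of Tables 5.40 and 5.41 assumes that sampling followed the protocol.

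**What to change.** In SAP 6.7.2:

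- **OSI:** replace the listing-only sentence with a summary by arm, with n, at Day 1, Day 35 and Day 84. State which eye is analysed. Add the plan's own ANCOVA (treatment plus Day 1 value) at Day 35 and Day 84.
- **HLA-DR:** apply the same ANCOVA to Day 84 AUF and percentage, and say that it replaces the generic rules of 5.2 for this endpoint. Extend the invalid-result rule in SAP 3.3 to AUF.
- **Both:** report the adjusted difference and 95% CI in PP and FAS, with n per arm, and label the comparisons exploratory because the subsets may be small. If normality is strongly violated, use the additional Wilcoxon rank sum test already in SAP 5.2. The documents give no AUF distribution, so they offer no basis for fixing a transformation in advance.
- **Table 5.41:** reconcile the OSDI cut-off in SAP 6.7.2 with that in Protocol 6.8.5 and SAP 2.5, then decide whether to keep the table. If it stays, state its method.
- **SAP 8.1:** add the matching tables.

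The cost is a few tables from data already collected. The downside is wide intervals and a few more unadjusted secondary comparisons.
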